12.2 Secondary Study End Points

- *L1/1.er and Upper Body Maximal Muscular Strength* will be assessed as a voluntary one-repetition maximum (1-RM) using the following exercises: (1) leg press, (2) chest press, and (3) seated row. These tests will be repeated twice and the heaviest weight lifted while adhering to strict technique and form will be used as the score.
- *Resting left ventricular function by 3-dimensional echocardiography (3DE)*: Three-dimensional transthoracic echocardiograms will be performed by experienced sonographers and acquired with commercially available equipment (Vivid 7 or E9, GE Healthcare, Milwaukee, WI).

Following completion of the 2DE, a full volume dataset will be acquired using a matrix array transducer with gated 4 beat acquisitions for assessments of left ventricular (LV) volumes by 3DE. A 3DE acquisition of the entire LV will be generally performed in <10 seconds. All assessments will be stored digitally for offline analyses performed using EchoPAC PC workstation (version BT11, GE 1Vledical, Milwaukee, WI).

Conventional 20 measurements of LV dimensions, Doppler, and diastolic function parameters will be performed and averaged over 3 cardiac cycles according to American Society of Echocardiography guidelines.³⁹⁻⁴¹

Left ventricular volumes and left ventricular ejection fraction (LVEF) by 3DE will be determined by manipulating the full volume dataset to derive conventional apical 4-, 3-, and 2-chamber views using TomTec offline analysis software (4D LV-Function, Unterschleisheim, Germany). After selection of reference points, a 3D endocardial contour will be automatically generated and manual adjustment will be performed as necessary. The resultant end-diastolic (EDV) and end-systolic volumes (ESV) will be used to calculate LVEF.⁴²

All resting echocardiography assessments will be conducted in Cardiology either at the Sidney Kimmel Center for Prostate and Urologic Centers or at the Main Campus or at the Rockefeller Outpatient Pavilion on 53rd Street, by a select group of sonographers in the Cardiology Service, using commercially-available GE Medical systems.

If any cardiac abnormalities are observed either prior to, during, or after the exercise test, all procedures will be immediately stopped. At this point, the physician on the floor will be asked to review the echocardiographic images to determine the appropriate course of action. The participant will not be allowed to leave the facility until such an examination has been

performed by the physician. All events will be recorded in the participant's REDCAP. The participant's attending oncologist will be informed of this event by email within 12 hours of occurrence.

- *Post VO_{2peak} Left Ventricular Function by 3-Dimensional Echocardiography (3DE):* Within 30 seconds of completion of the cardiopulmonary exercise test, subjects will be placed in the supine position and 2DE grayscale images will be obtained in the apical 4-, 3-, and 2-chamber views. Wall motion scoring index (WMSI) will be calculated at rest and post-exercise using the 17 segment model by adding the individual segment scores (1 = normal; 2 = hypokinesia; 3 = akinesia; 4 = dyskinesia) and dividing by number of segments scored.³⁹

30 LV volumes and LVEF will be calculated offline using the modified Simpson's biplane method. Cardiac output will be calculated as the product of LV stroke volume and heart rate, indexed to body surface area (BSA).

All post-exercise echocardiography assessments will be conducted in Cardiology either at the Sidney Kimmel Center for Prostate and Urologic Centers or at the rv1ain Campus or at the Rockefeller Outpatient Pavilion on 53rd Street, by a select group of sonographers in the Cardiology Service, using commercially-available GE Medical systems.

If any cardiac abnormalities are observed after the exercise test, all procedures will be immediately stopped. At this point, the physician on the floor will be asked to review the echocardiographic images to determine the appropriate course of action. The participant will not be allowed to leave the facility until such an examination has been performed by the physician. This event will be recorded in the participant's REDCAP. The participant's attending oncologist will be informed of this event by email within 12 hours of occurrence.

- *Regional Arterial Stiffness:* Conduit regional artery stiffness of the entire aorta will be assessed non-invasively by measuring carotid-femoral pulse wave velocity (PWV) using 2 hand-held tonometers (SPT-301 Millar Instruments, Houston, TX).

Carotid and femoral artery waveforms will be recorded simultaneously with the mechanotransducers directly applied to the skin over the greatest area of pulsation. Twenty consecutive reproducible beats will be collected simultaneously at both sites, with a concurrent electrocardiograph to obtain R-R intervals.

Pulse transit time will be determined as the difference in time from R interval to systolic upstroke at each location. Systolic upstroke will be determined by identifying the foot or "notch" of the blood pressure waveform. This will be done by applying a band pass filter between 5-30 Hz, selecting the minimum value of the filtered signal.

Pulse distance will be determined using anthropometric measuring tape subtracting the distance from carotid measurement to sternal notch from the distance fr001 sternal notch to femoral pulse measurement. This method has been shown to be the optimal non-invasive

measurement compared to invasive measure. PWV will then be determined by taking the pulse transit time/distance.

All arterial stiffness measurements will be conducted in Cardiology Service space either at the Sidney Kimmel Center for Prostate and Urologic Centers or at the rvlain Campus or at the Rockefeller Outpatient Pavilion on 53rd Street, or at the Sidney Kimmel Center for Prostate and Urologic Cancers, on ExOnc equipment specifically designated for research purposes. All tests will be conducted by ExOnc exercise physiologists .

- *Flow Mediated Dilation:* Peripheral artery flow-mediated dilatation will be performed on the left arm with the subject in a supine position with the forearm extended and slightly supinated. A rapid inflater blood pressure cuff will be placed on the forearm just distal to the antecubital crease and the brachial artery will be imaged using high-resolution B-mode ultrasound and a 7.5MHz linear array transducer (Terason, t3200). Ten-second r-wave triggered digital clips (artery diastole) will be captured at baseline (following 10min of supine rest), during five minutes of forearm occlusion, and a 120 sec r-wave triggered digital clip will be captured beginning at cuff deflation (hyperemia) as previously described.⁴³ Offline analysis using specialized software (Brachia! Tools, Medical Imaging Applications, Illinois) will permit for identification of peak dilation and dilation at specific pre-specified time points (60, 120 sec).⁴⁴ Due to the potential confounding effects, patients will be asked to withhold vasodilatory substances (e.g., caffeine, exercise) 24 hours prior to assessment.
- *Body Composition:* Body composition will include percent body fat, fat mass (FM), and lean body mass (LBM) evaluated by dual-energy x-ray absorptiometry (DEXA) using a GE Lunar Prodigy multiple detector fan-beam densitometer.
- *Pulmonary Function* will be determined using standard spirometry. All measures will be performed in a sitting position according to the American Thoracic Society guidelines.⁵³
- *Functional Performance Measures:* Assessment of functional measures will include the performance on the following tests:
 - *Short Physical Performance Battery (SPPB):* The SPPB is a brief performance-based functional mobility measure that includes measures of standing balance, usual pace walking speed, and ability and time to rise from a chair 5 times.
 - *Six-Minute Walk Test (6MWT):* The 6MWT is a valid responsive, interpretable self-paced test that quantifies functional exercise capacity in terms of the distance walked in six minutes.
 - *Chair-stand test:* Chair-stand test (number of sit to stands a subject can complete in 30 seconds) will be used as a measure of functional lower body strength.

- o *Timed Up and Go (TUG)*: TUG is a timed measure of balance and functional mobility. The test requires the patient to rise from a standard armchair, walk 3 meters at a comfortable pace, walk back to the chair, and sit down.

All functional performance measurements will be conducted by ExOnc exercise physiologist at the Sidney Kimmel Center for Prostate and Urologic Cancers or Sillerman Center for Rehabilitation.

- *Patient-Reported Outcomes*: Patient-reported outcomes will be assessed using a patient-administered questionnaire to assess quality of life, fatigue, pain, and sleep quality.
 - o *Quality of Life* (QOL) will be assessed by the Functional Assessment of Cancer Therapy-Lung (FACT-L) scale. The FACT-L contains subscales for physical (7 items), functional (7 items), emotional (6 items), and social or family well-being (7 items) that comprise the FACT-General (FACT-G) scale, plus a lung cancer subscale (7 items). The five subscales will be summed to obtain the FACT-L score (all 34 items; total score of 136). We will also compute the FACT-G score (27 items, excluding the breast cancer subscale; total score of 108).⁴⁵ All items are rated on a 0 to 4 Likert scale, using the following response format: 0 = not at all; 1 = a little bit; 2 = somewhat; 3 = quite a bit; 4 = very much. We will also calculate the Trial Outcome Index (TOI). The TOI is the sum of the Physical Well-Being (PWB), Functional Well-Being (FWB), and Lung Cancer subscales. Respondents are asked to respond to each question as it applies to the past 7 days. Higher scores on the FACT-L indicate higher QOL. Internal consistency for the FACT-G and FACT-L is established.
 - o *Fatigue* will be assessed using the 13-item FACT-fatigue scale for the assessment of fatigue in cancer patients.⁴⁶ The 13 items will be summed to obtain the total fatigue score (total score of 52). All items are rated on a 0 to 4 Likert scale, using the following response format: 0 = not at all; 1 = a little bit; 2 = somewhat; 3 = quite a bit; 4 = very much. Respondents are asked to respond to each question as it applies to the past 7 days. Higher scores on the FACT-fatigue indicate higher fatigue. Internal consistency for the FACT-fatigue is well established.⁴⁶
 - o *Pain* will be assessed using the 10-item Brief Pain Inventory (BPI) which was designed to measure multiple clinically relevant aspects of pain such as pain intensity and interference from pain in cancer populations.⁴⁷ The BPI assesses for the presence of pain, pain intensity (i.e., worse, least, average, current) and functional interference from pain (i.e., activity, mood, walking ability, normal work, relations with others, sleep, and life enjoyment). It also catalogues the types of pain medications being used, and the percentage of pain relief obtained from medications.

The BPI uses a mixture of item types. Items 1-3 querying about the presence of pain is a dichotomous "yes", "no". Items 4-7 (intensity items) utilize a 0 (no pain) to 10 (pain as bad as you can imagine) 11-point rating scale. Item 8 (percentage of pain

relief) ranges from 0% (no relief) to 100% (complete relief). Item 9 inquires about the effectiveness of pain medication (as appropriate). Item 10 (a-g) inquires about interference using an 11-point numeric rating scale. Each item ranges between 0 (does not interfere) to 10 (completely interferes). Respondents are asked to respond to each question as it applies to the past 7 days.

While some of the items represent single item values, pain intensity, indexed by the "Pain Severity Score" is calculated by obtaining the mean of the 4 pain intensity items. The Pain Interference Score is obtained by calculating the mean of the 7 interference items.

The "Pain Severity Score" has a maximum value of 10 (i.e., "pain as bad as you can imagine" and a minimum value of 0 (i.e., "No pain"). The Pain Interference Scale similarly has a maximum value of 10 (i.e., "Completely Interferes") to 0 (i.e., "Does not Interfere").

Internal consistency for the Pain Severity Score and for the Interference scale has been reported as being 0.85 and 0.88 respectively⁴⁷

- o *Sleep Quality* will be assessed by the Pittsburgh Sleep Quality Index (PSQI).⁴⁸ The PSQI assesses sleep disturbance over the past month. The PSQI is an 9-item self-report questionnaire. The PSQI uses a mixture of item types. Items 1-4 are open-ended questions that query about sleep habits. All remaining items are scored on a 4-point Likert scale which range from 0 (not during the past month) to 3 (3 or more times a week). The items produce seven component scores: sleep duration, sleep disturbance, sleep latency, daytime disturbance, habitual sleep efficiency, sleep quality, and use of sleep medications. The sum of these component scores yields a measure of global sleep quality which ranges from 0 to 21. Reliability measures indicate that the PSQI generally has acceptable internal consistency ($\alpha = .80$ to $.85$) and test-retest reliability ($r = .85$ to $.87$).⁴⁸
- o *Exercise behavior* will be assessed by the leisure score index (LSI) of the Godin Leisure-Time Exercise Questionnaire (GLTEQ) which is used to measure the minutes and type of exercise per week.^{49,50} The LSI contains three questions that assess the average frequency of mild, moderate, and strenuous intensity exercise during free time in a typical week over the past month. In this protocol, participants will be asked to report their average weekly exercise over the past month. We will also ask for average duration within each exercise intensity. An independent evaluation of this measure found its reliability and validity to compare favorably to nine other self-report measures of exercise based on various criteria including test-retest scores, objective activity monitors, and fitness indices (Jacobs et al. 1993). The LSI demonstrated a one-month test-retest reliability of $.62$ and concurrent validity coefficients of $.32$ with an objective activity indicator (CALTRAC accelerometer), $.56$ with $VO_{2\max}$ (as measured by expired gases), and $-.43$ with % body fat (as measured by hydrostatic weighing).

- o *Physical Functioning* will be assessed using the physical functioning subscale (PF) of the Short-Form (SF) 36.⁵¹ The physical functioning subscale is a 6-item self-report questionnaire. The PF uses a mixture of item types. Item 1 queries about overall health, scored on a 5-point scale ranging from excellent to poor. Item 2 queries about limitations to normal activities of daily living including participation in vigorous and moderate activities. All items are rated on a 3-point Likert scale from yes, limited a lot to no, not limited at all. Item 3 queries about limitations relating to work over the past 4 weeks using a dichotomized response (yes vs. no). Item 4 queries about bodily pain over the past 4 weeks ranging from none to extremely. Item 5 queries about pain during the normal work week ranging from not at all to extremely. Finally, item 6 asks 4 statements asking about general health perceptions scored on 5-point Likert scale ranging from definitely true to definitely false. The sum of item 2 yields a measure of physical functioning ranging from 0 to 20. Other items will be considered and summed as single items. Higher scores indicate higher physical functioning. The SF-36 has well established internal consistency and test-retest reliability.⁵¹
- *Safety* will be evaluated by the type and prevalence of adverse events during study-related assessments as well as exercise training sessions. The type and nature of SAEs considered in this trial include those DLTs listed in Section 9.3 as well as those events listed in Section 11.1 (the unanticipated but possible adverse events associated with CPET, 1RM, aerobic training or resistance training).

Tracking and monitoring of exercise-related adverse events will be assessed using the following methods:

1. Stringent monitoring and recording (in the patient REDCAP) of physiologic outcomes and vital signs (e.g., heart rate, blood pressure, etc.) prior to, during, and following every intervention session.
2. At the beginning of each week, the exercise specialist will spend the first 10 minutes of every session discussing any potential negative side-effects of the intervention assignment and any injuries that may have occurred. All events will be recorded in the patient REDCAP.
3. Early stopping rules in response to a differential higher frequency of adverse events in a particular study group as identified in planned interim analyses (see **Section 14.0**).

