2.2 Secondary Objectives

- To compare the effects on one-repetition maximum
- To compare the effects on resting and exercise cardiac function
- To compare the effects on pulmonary function
- To compare the effects on arterial stiffness

- To compare the effects on endothelial function (Flow Mediated Dilation)
- To compare the effects on body composition
- To compare the effects on functional measures of performance
- To compare the effects on patient-reported outcomes (e.g., quality of life, fatigue), and
- To collect and bank blood samples for future correlative studies.

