14.2 Primary and Secondary End Point Analyses

14.2.1 Primary End Point Analysis: The primary analysis will compare the efficacy of different types of exercise training modalities, relative to progressive stretching (attention control group), on $\text{v}_{\text{O}_2\text{peak}}$ in lung cancer.

An intent-to-treat statistical analysis will be conducted. Baseline characteristics will be compared using the Fisher exact test for categorical variables or a Wilcoxon rank sum test for continuous variables. The primary end point comparison will be analyzed using a multiple linear regression model to test for differences among and between the study arms in $\text{v}_{\text{O}_2\text{peak}}$ from baseline to follow up. The multiple linear regression model will include the baseline value of $\text{v}_{\text{O}_2\text{peak}}$, the stratification variables (i.e., chemotherapy treatment and sex), and study site.

In the absence of evidence to the contrary, multiple imputation strategies for missing Week 17 $\text{v}_{02\text{peak}}$ data will be performed assuming data were missing at random using linear regression. Results will be aggregated over 20 imputed sets using the variance formula by Rubin. In addition, a per-protocol analysis will be performed using a multiple linear regression model to test for differences among and between the study arms in $\text{v}_{02\text{peak}}$ from baseline to the post-intervention assessment (Week 17) on the basis of exercise attendance and adherence to the supervised exercise training in Arms A to C (<80% versus 80%).

14.2.2 Secondary End Point Analyses: As for the primary end point, the intention-to-treat principle will be employed for analysis of all secondary end points. Multiple linear regression models will be used to test for differences among and between the study arms in secondary end points from baseline to the postintervention assessment (Week 17). The multiple linear regression model will include the baseline value of $\text{v}_{02\text{peak}}$, the stratification variables (i.e., chemotherapy treatment and sex), and study site.

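### The written formula for pulse wave velocity is upside down: transit time over distance is the reciprocal of a velocity

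*Combined protocol and SAP*

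**What the plan says.** Section 2.2 lists the endpoint among the secondary objectives: "To compare the effects on arterial stiffness". Section 12.2 says that stiffness of the whole aorta is "assessed non-invasively by measuring carotid-femoral pulse wave velocity (PWV) using 2 hand-held tonometers", and then gives the two ingredients and the rule that combines them:

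- A time: "Pulse transit time will be determined as the difference in time from R interval to systolic upstroke at each location".
- A length: "Pulse distance will be determined using anthropometric measuring tape subtracting the distance from carotid measurement to sternal notch", taken from the notch-to-femoral distance.
- The rule: "PWV will then be determined by taking the pulse transit time/distance".

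Table 2 in Section 8.0 repeats the rule word for word. No other place in the document gives the ratio the other way up, a unit for PWV, or a statement of which direction means stiffer.

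For the analysis, Section 14.2.2 says: "Multiple linear regression models will be used to test for differences among and between the study arms in secondary end points", covering baseline to Week 17.

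**The concern.** A velocity is a distance divided by a time. The plan names a velocity, defines a time and a distance, and then divides them the wrong way round. These two sentences are the only derivation rule given for this endpoint.

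Anyone who programs the rule as written gets a variable labelled PWV that falls when the wave speeds up. Using PWV as the measure of stiffness implies that a faster wave means a stiffer artery. An arm whose arteries became less stiff could therefore be described as having become stiffer. A summary on the reciprocal scale also cannot be turned back into a mean in m/s.

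The trial's history adds a reason to check. Section 1.0 plans to pool 93 participants randomized at the first institution with 67 at the second. If PWV was collected at both and derived differently, the additive study-site term in the Section 14.2 model would not repair the mismatch, because it cannot undo a reversed, non-linear scale.

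**Working it through.** The plan states no figure to reproduce. The check is one of units, then of direction, then of what happens to means. The documents give no path lengths, transit times or velocities, so every numerical value below is an assumption chosen for illustration.

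**1. Units.** Transit time T is in seconds and pulse distance D in metres (Section 12.2).

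- As written: T / D, in s/m.
- A velocity: D / T, in m/s.
- Hence written quantity = 1 / PWV exactly.

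**2. Direction for one patient, with the path fixed at an assumed 0.50 m.**

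| T (s) | D / T (m/s) | T / D (s/m) |
|---|---|---|
| 0.080 | 6.25 | 0.160 |
| 0.055 | 9.09 | 0.110 |
| 0.050 | 10.0 | 0.100 |
| 0.040 | 12.5 | 0.080 |

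A transit time lengthening from 0.050 to 0.055 s gives:

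- PWV: (9.09 − 10.0) / 10.0 = −9%.
- Written quantity: (0.110 − 0.100) / 0.100 = +10%.

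Over assumed paths of 0.45 to 0.60 m and transit times of 0.040 to 0.080 s, PWV runs from 0.45 / 0.080 = 5.6 to 0.60 / 0.040 = 15.0 m/s. The written quantity runs the other way, from 0.178 down to 0.067 s/m. For positive values the ordering is always reversed (rank correlation −1).

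**3. Direction for a mean.** The regression compares arms, and a mean of reciprocals is not the reciprocal of a mean. Take an arm of two patients with assumed velocities:

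| Patient | PWV before to after (m/s) | Change (m/s) | Written quantity before to after (s/m) | Change (s/m) |
|---|---|---|---|---|
| 1 | 6 to 7 | +1.0 | 0.1667 to 0.1429 | −0.0238 |
| 2 | 14 to 12.5 | −1.5 | 0.0714 to 0.0800 | +0.0086 |
| Mean | | −0.25 | | −0.0076 |

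Each patient's change reverses, yet both means fall. If nobody in a comparison arm changed, the unadjusted between-arm difference would equal these means, so it would not reverse either. Reversal is the usual result for group summaries, not a certainty.

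**4. Scale.** In a simulation of velocities drawn from a normal distribution with mean 9 and SD 2 m/s (values above 4 kept), the Pearson correlation between PWV and its reciprocal was about −0.95. The mean velocity was 9.03 m/s. Inverting the mean of the reciprocals gave 8.58 m/s, which is 0.45 m/s lower. A linear model on s/m would therefore differ from one on m/s in more than sign.

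**5. Recovery.** Each patient's value at each visit can be inverted without loss (1 / 0.110 = 9.09 m/s) and the model refitted. Inverting an arm mean is not enough, as step 4 shows.

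**The case against.** The strongest case on the other side is that this is a slip of wording with no practical effect. The quantity is named a velocity on the page. On the illustration above, a literal result would be about a hundredfold smaller than the velocity (0.100 against 10.0), which should be noticed. The slash may be loose shorthand for using time and distance. The endpoint is one of many secondary ones, and the primary VO2peak analysis, the Holm procedure and the sample size do not depend on it.

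Much of that stands, and it limits the weight of the point. It does not remove the error. If the slash is shorthand, the plan gives no formula at all, and the same sentence still has to be written.

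A reader might make three stronger inferences that the documents do not support:

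- *Every arm-level result would be reversed.* This is true of each patient's change, but the two-patient example shows that it need not hold for means.
- *The derivation is by hand, so nothing could override the formula.* Both descriptions include a band-pass filter step to locate the foot of the waveform, which implies some computation. The documents name no program for the final ratio, so neither correct software nor hand calculation is established.
- *Stiffness data have been miscalculated.* Nothing shows this. Section 16.02 says that first-site participants completed study procedures, but does not list arterial stiffness among the data collected there.

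**Conclusion.** The secondary endpoint definition is wrong as written, in Section 12.2 and in Table 2. By the plan's own definitions the stated ratio is the reciprocal of PWV. If it were followed literally, each patient's change would have the opposite sign, mean changes and between-arm differences would generally reverse, and the regression would be run on a non-linear transform of the intended variable.

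The unit argument needs no assumption beyond the meaning of velocity. The numerical sizes rest on assumed paths, times and velocities. That higher PWV means a stiffer artery is not stated in the documents; it is implied by their choice of PWV as the stiffness measure.

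The defect is confined to the written definition of one secondary endpoint and is recoverable from patient-level values. It should be corrected before the stiffness analysis is run, and it does not bear on the primary result.

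**What to change.** In Section 12.2 and in Table 2, replace the sentence with: *PWV (m/s) will be calculated as pulse distance divided by pulse transit time (femoral minus carotid R-to-foot time); higher values indicate greater stiffness.*

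Then confirm that the derived variable uses this ratio in all records, including those from the first site if PWV was collected there. If any values turn out to be in s/m, invert them patient by patient and visit by visit before any averaging or modelling.

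The cost is one sentence in two places and a check of the derivation. No new data are needed.
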